7. PARTICIPANT SAFETY AND WITHDRAWAL

a. RISK MANAGEMENT AND SAFETY

In this prospective observational cohort study, there will be no deviation from standard of care treatment.

Participants will be required to have serial additional blood sampling, performed when blood tests for the standard of care for LT occur wherever possible. This is the reduce the need for additional venepuncture, and is anticipated to be highly feasible due to the frequency of blood tests required for the standard of care post LT.

Participants may be subjected to mild physical (pain, bruising, dizziness) or psychological distress (anxiety) during venepuncture. They will be informed this low risk prior to enrolment, and provided with access to medical or counselling services if required.

b. HANDLING OF WITHDRAWALS

Participants who withdraw from this study will have the opportunity to have a withdrawal interview with the research coordinators, in order to voice their concerns and to receive

answers for any questions. Unless specified by the participant, already collected data will be kept for analysis and future research purposes. However, in cases where initial consent has been obtained from their person responsible and the patient then wishes to withdraw this consent, all of their data collected for research purposes will be securely destroyed.

c. Replacements

Withdrawn participants will be replaced in this study

8. STATISTICAL METHODS

a. SAMPLE SIZE ESTIMATION & JUSTIFICATION

We propose enrolling a total of 210 LT recipients during a three-year recruitment period. This timeframe is anticipated to be easily feasible as the LTU performs an average of 75 adult LTs each year. Most recipients will fulfil the trial's inclusion and exclusion criteria; hence non-eligibility (including refusal of informed consent) is anticipated to be low (about 5%). In addition, lost-to-follow-up (including death) is anticipated to be very low (about 1-2%) during the 12-month follow-up².

In preliminary research from Austin Health¹⁶, 31% of the recipients experienced tBPAR as the first event after LT while 41% experienced a 'probable'/'definite' infective complication as the first event after LT, both within a 12-month follow-up period. To be conservative, we assume 30% of our recruited recipients will experience at least one tBPAR and 40% at least one infective complication. The sample size of 210 LT recipients will allow us to estimate a fair AUC of 0.7 using a two-sided 95% confidence interval with precision \pm 0.081 for tBPAR and \pm 0.075 for infection and a good AUC of 0.8 with a precision of \pm 0.075 for tBPAR and \pm 0.069 for infection^{21,22}.

b. POWER CALCULATIONS

This sample size will provide a power of 99.7% to show that the combination has any ability to discriminate between those with and without tBPAR and 99.9% power between those with and without infection, (null hypothesis AUC of 0.5), assuming that we observe a fair AUC of 0.7 with 5% alpha²¹.

c. STATISTICAL METHODS TO BE UNDERTAKEN

All participants will be included in the final analyses. Diagnostic performance of QFM and dscfDNA combined for the first tBPAR and the first 'probable'/'definite' infective complication will be assessed by evaluation of sensitivity, specificity, the positive and negative predictive value and diagnostic accuracy. Diagnostic accuracy will be evaluated by determining the AUC and two-sided 95% confidence interval. Given that QFM and dscfDNA outcomes are measured repeatedly over 12 months, we will initially summarise these outcomes across time-points using the average, nadir, standard deviation and slope and fit a logistic regression model.

Next, we will look at moving average, moving standard deviation, and change of slope and fit a mixed logistic regression model. Finally, a joint model for longitudinal tBPAR, respectively longitudinal infective complications, and QFM, dsfDNA and LFT outcomes will be explored. This model will allow investigation of the temporal dynamics of rejection and infection, and evaluate the usefulness of QFM and dscfDNA for monitoring purposes²³.

We will compare the AUC of using QFM alone or dscfDNA alone versus the combination. An optimal threshold of QFM and dscfDNA in identifying recipients at risk of tBPAR or infection will be established. A detailed statistical analysis plan will be prepared prior to locking of the

database.

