4. STUDY OBJECTIVES

a. HYPOTHESIS

The primary hypothesis is that the QFM-dscfDNA tests can be used to accurately diagnose the occurrence of acute rejection and infective complications after LT.

The secondary hypotheses are that the QFM-dscfDNA tests can be used to:

- Predict acute rejection and infective complications.
- Monitor treatment responses.
- Improve healthcare resource utilisation.

b. STUDY AIMS

- To examine if the QFM-dscfDNA tests can be used to accurately diagnose acute rejection and infective complications after LT.
- To examine if the QFM-dscfDNA tests can be used to predict acute rejection or infective complications, monitor treatment responses, and improve healthcare resource utilisation.

c. OUTCOME MEASURES

i. DEFINITION OF CLINICAL EVENTS:

- Rejection: The gold standard for diagnosing acute rejection is based on histopathologic grading on liver biopsy. It is often difficult to differentiate mild rejection from ischemia-related cholestasis early after LT and clinical evaluation may lead to observation rather than active treatment if temporal improvement is demonstrated. We thus employed the strict definition requiring consistent histology and treatment of rejection (tBPAR), an acceptable standard for clinical trials^{18,19}.
- Infective complications: Infection endpoints will be defined according to the criteria of 'no', 'probable' or 'definite' infection derived from the international sepsis forum consensus conference on '*Definitions of Infection in the Intensive Care Unit*^{'20}.

i. VARIABLES TO BE MEASURED:

- Standard of care clinical variables: Donor and recipient factors such as donor risk index, model for end-stage liver disease score, waiting list time, primary indication for transplantation, operative factors and immunosuppression regimens can influence post LT outcomes. These characteristics will be prospectively recorded for analysis.
- Standard of care blood tests: Routine blood tests including full blood count (FBE), urea and electrolytes (UEC), LFTs and serum drug levels are used for clinical decision making as a standard of care. The results of each test will be prospectively recorded.

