- QFM: Recipient blood samples will be processed within eight hours of venesection. The blood samples will be stimulated with the QFM immune ligands anti-CD3 and R848¹⁴, incubated overnight at 37 °C and fractionated. The plasma component will then be stored at -80 °C. A batched analysis of the stored plasma will be performed at the end of the 12-month follow-up using ELISA to quantify IFNγ as IU/m, so results will not influence the decision-making of the treating clinicians.
- dscfDNA: Recipient blood samples will be processed within three hours of venesection. The blood samples will be fractionated into the leukocyte-rich 'buffycoat' and plasma components. Donor blood samples will be obtained during organ procurement, in accordance with the Human Research Ethics Committee for Donate Life and the Australian Red Cross Blood Services (application in progress). All samples will be stored at -80 C. Genomic DNA will first be extracted from the buffy coats of the organ donors and the pre-transplant recipient. High resolution melting analyses will be used to genotype each donor-recipient pair using a panel of small biallelic deletion/insertion polymorphisms¹⁶. This step will be performed once for each donor-recipient pair to determine a set of allelic sequences that are present in the donor and absent in the recipient for the detection of dscfDNA. Subsequently, we will utilise our rapid and readily performed methodology to quantify dscfDNA¹⁷. Our novel assay design enables the amplification of dscfDNA using allelic breakpoints that are only present in donor-specific alleles. Combined with the Bio-Rad droplet digital polymerase chain reaction (PCR) platform, dscfDNA can be measured with unprecedented accuracy in the recipient's blood, in copies/mL of recipient plasma. As with QFM, the samples of each recipient will be batched for analysis at the end of the 12-month follow-up, so results will not influence the decision-making of the treating clinicians.
- Health expenditure: The costs associated with inpatient and outpatient healthcare resource usage, investigations medications and the QFM-dscfDNA tests will be

retrieved from the Austin Health Department of Finance, Austin Health as well as the Medicare Benefits Schedule (MBS) and Pharmaceutical Benefit Scheme (PBS).

ii. PRIMARY ENDPOINTS:

The accuracy of QFM and dscfDNA, alone and in combination, compared to LFTs to diagnose:

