- The first episode of tBPAR, as measured by the area under the receiver operator curve (AUC).
- The first episode of infective complication, as measured by the AUC.

iii. SECONDARY ENDPOINTS:

- The accuracy of QFM and dscfDNA, alone and in combination, in predicting the occurrence of imminent tBPAR and infective complications before clinical manifestation of the event.
- The performance of QFM and dscfDNA, alone and in combination, in monitoring treatment responses of tBPAR and infective complications, as compared to routine blood tests.
- Healthcare expenditures and cost-effectiveness of QFM-dscfDNA, as measured using hospital, PBS and MBS data.

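### Both primary endpoints compare the new tests' AUC with LFTs, but Section 8 gives no precision, power or AUC analysis for that comparison; the 99.7% and 99.9% are for AUC against 0.5

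*Protocol*

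**What the plan says.** - **Endpoint.** Protocol Section 4.c, Primary endpoints: "The accuracy of QFM and dscfDNA, alone and in combination, compared to LFTs to diagnose" the first tBPAR and the first infective complication, each measured by AUC. The comparator is part of the endpoint.
- **Hypothesis.** Section 4.a: "The primary hypothesis is that the QFM-dscfDNA tests can be used to accurately diagnose the occurrence of acute rejection and infective complications after LT". LFTs are not named.
- **Sample size.** Section 8.a: "We propose enrolling a total of 210 LT recipients during a three-year recruitment period", and "we assume 30% of our recruited recipients will experience at least one tBPAR and 40% at least one infective complication". N is justified by the 95% CI half-width of a single AUC: 0.081 (tBPAR) and 0.075 (infection) at AUC 0.7, and 0.075 and 0.069 at AUC 0.8.
- **Power.** Section 8.b: "a power of 99.7% to show that the combination has any ability to discriminate between those with and without tBPAR", and 99.9% for infection. The condition attached is "null hypothesis AUC of 0.5), assuming that we observe a fair AUC of 0.7 with 5% alpha".
- **Analysis.** Section 8.c plans the AUC of the combination with a two-sided 95% CI. The one AUC comparison it names is: "We will compare the AUC of using QFM alone or dscfDNA alone versus the combination". LFTs enter Section 8 once, as one of the longitudinal outcomes in a joint model that is to be explored for temporal dynamics and monitoring.

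**The concern.** Endpoint, power statement and named analysis do not address the same question. Showing that an AUC exceeds 0.5 means that a test discriminates at all. It does not show that the test does better than the blood tests already in use. The protocol's introduction rests on the poor specificity of LFTs and on sparing imaging and biopsy, and a positive result is meant to lead to a randomised trial. For that decision the comparison with LFTs is the informative one, and Section 8 gives it no estimator, no precision and no power. A team following Section 8.c to the letter could report a combination AUC clearly above 0.5 and leave the comparison in Section 4.c to be specified late. The choice of LFT variable and comparison could then be made with the results in view.

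**Working it through.** **Inputs from the protocol.** N = 210. At 30% tBPAR there are 63 with and 147 without the event; at 40% infection, 84 and 126. Alpha is 5%, the null AUC 0.5 and the alternative 0.7. Sidedness of the power is not stated; two-sided is used here, as for the confidence interval.

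**Step 1: the stated precision.** Binormal variance, with a = 1.414·Φ⁻¹(A) and k = n0/n1:

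V(A) = 0.0099·exp(−a²/2)·[(5a² + 8) + (a² + 8)/k]/n1

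The half-widths 1.96·√V are:
- tBPAR: 0.0813 (A = 0.7) and 0.0754 (A = 0.8)
- infection: 0.0752 and 0.0690

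All four match Section 8.a.

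**Step 2: the stated power.** Hanley-McNeil variance, with Q1 = A/(2 − A) and Q2 = 2A²/(1 + A):

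V(A) = [A(1 − A) + (n1 − 1)(Q1 − A²) + (n0 − 1)(Q2 − A²)]/(n1·n0)

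Power = Φ[(0.2 − 1.96·SE(0.5))/SE(0.7)]
- tBPAR: (0.2 − 1.96 × 0.04357)/0.04136 = 2.77, power 99.72%
- infection: (0.2 − 1.96 × 0.04076)/0.03770 = 3.19, power 99.93%

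The binormal variance gives 99.76% and 99.93%. With 2% loss (N about 206) the results are still 99.7% and 99.9%. The figures are right for their own hypothesis.

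**Step 3: the comparison in Section 4.c.** Both AUCs come from the same patients, so

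SE_diff² = V1 + V2 − 2r·√(V1·V2), power = Φ[(A1 − A2)/SE_diff − 1.96]

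The protocol gives no LFT AUC and no r; both are assumed. Example for tBPAR, 0.70 vs 0.60, r = 0.5: SE_diff² = 0.001711 + 0.001904 − 0.001805 = 0.001810, so SE_diff = 0.0425. Then 0.10/0.0425 − 1.96 = 0.39, power 65%, with a half-width for the difference of 1.96 × 0.0425 = 0.083.

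| Combination vs LFT AUC | Event | r = 0 | r = 0.5 | r = 0.7 | Simulated, r = 0 to 0.7 |
|---|---|---|---|---|---|
| 0.70 vs 0.65 | tBPAR | 13% | 22% | 34% | 14-33% |
| | infection | 15% | 25% | 39% | 16-37% |
| 0.70 vs 0.60 | tBPAR | 38% | 65% | 86% | 41-86% |
| | infection | 44% | 73% | 91% | 46-89% |
| 0.80 vs 0.70 | tBPAR | 44% | 73% | 91% | 50-92% |
| | infection | 52% | 81% | 95% | 56-95% |
| 0.80 vs 0.60 | tBPAR | 94% | >99% | >99% | 96-100% |
| | infection | 97% | >99% | >99% | 98-100% |

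The three middle columns use the formula, where r is the correlation between the two AUC estimates. The last column simulates bivariate normal markers with correlation r and applies the DeLong test (4,000 data sets per cell). The formula runs up to about six points lower at r = 0. The simulated mean 95% CI half-width for the AUC difference is about 0.06 to 0.11.

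By the formula, the gain detectable with 80% power is about 0.09 to 0.16 (tBPAR) and 0.08 to 0.15 (infection) for an LFT AUC of 0.6 to 0.7.

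**The case against.** Several points on the other side stand.

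- **Section 8.b states its null openly** and nowhere presents 99.7% as power against LFTs. The figure is not an error.
- **N rests on precision, not on this power.** Section 8.a justifies 210 by CI half-widths, and Section 8.b only adds what that number also provides.
- **The hypothesis in Section 4.a does not name LFTs.** An AUC with its CI goes some way to answering it, so the primary question is stated in two ways. That makes alignment part of the fix. It does not remove LFTs from the endpoint, and beating 0.5 falls short of accurate diagnosis too.
- **A detailed SAP is promised.** The test, the matching of sample times and similar detail may properly wait for it. The LFT comparison is declared in Section 4.c and LFT results are recorded prospectively, so a reader might infer that the comparison will never be made; the protocol does not support that. But no SAP can make 99.7% the power of an endpoint to which it does not refer.

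A reader might also infer that the study is underpowered for its primary endpoint. The protocol does not show this. Its own good AUC of 0.8 against an LFT AUC of 0.6 would give about 95% power or more, and a gain of 0.10 with correlation 0.7 gives about 85 to 95%. Nor does the protocol give a figure showing that LFTs themselves would beat 0.5, and the point does not need one.

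**Conclusion.** The point holds as a mismatch between Section 4.c and Section 8. The endpoint is a comparison with LFTs; the stated precision is for one AUC, the stated power is against 0.5, and the only named AUC comparison leaves LFTs out. The 99.7% and 99.9% are correct for their own null and are not the power for the primary endpoint as defined.

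No single corrected figure exists. At 63/147 and 84/126, two-sided 5%, power against LFTs is about 13-40% for a gain of 0.05 (0.70 vs 0.65), about 41-95% for a gain of 0.10, and about 95-100% for 0.80 vs 0.60. These ranges rest on assumed LFT AUCs of 0.60 to 0.70, assumed marker correlation of 0 to 0.7 and normally distributed markers. What they establish is that the answer depends on inputs the protocol does not state.

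**What to change.** 1. **Section 8.c:** name the paired AUC difference from LFTs, with a 95% CI, as the primary analysis, separately for first tBPAR and first infection. Take the combination first, then each test alone, since the endpoint covers all three. The choice between DeLong and bootstrap can go to the SAP.
2. **Section 8.b:** say that 99.7% and 99.9% apply only to AUC against 0.5. Add the expected CI half-width or power for the LFT comparison over a stated range of LFT AUC and correlation.
3. **Section 4.a:** align the primary hypothesis with the endpoint.

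The cost is wording and a less favourable stated figure. LFTs are already recorded, so no extra patients or samples are needed. The change should be made before the batched assay results are analysed, so that the comparator is not chosen with results in view.

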LFTs are extremely sensitive tests for organ injury but have poor specificity for LT complications⁷. As a screening tool, they can lead to a series of radiological and endoscopic investigations that often culminate in an invasive liver biopsy to confirm the clinical event⁸. Acute rejection is treated with increased doses of immunosuppressants while infection necessitates dosage reduction. This relatively 'reactive' approach precludes preventive intervention by predictive adjustments.

Researchers at Austin Health have shown that the use of an immune monitoring blood test, QuantiFERON-Monitor (QFM), identifies recipients at risk of early rejection or infective complications. Austin Health researchers have also developed a novel blood test to rapidly measure organ injury using donor-specific cell-free DNA (dscfDNA).

We propose a prospective observational cohort study of 210 patients who are LT recipients followed up for 12-months to determine the utility of combining the two blood tests (QFM-dscfDNA) in monitoring and managing immunosuppression post LT. Our primary hypothesis is that the QFM-dscfDNA tests can be used to accurately diagnose the occurrence of rejection or infective complications after liver transplantation. The secondary hypotheses are that QFM-dscfDNA tests can be used to predict acute rejection or infective complications, monitor treatment responses and improve healthcare resource utilisation.

There is a clear and urgent need for accurate clinical tools to personalise immunosuppression. Confirmation of our hypotheses facilitates a "predictive" rather than the current "reactive" approach to immunosuppression. Our approach can potentially minimise the need for complex diagnostic tests including ultrasound, computed tomography, magnetic resonance imaging, endoscopy and liver biopsies - with significant clinical and economic benefits.

If positive, the findings of this study will lead to a prospective randomised multi-centre trial comparing the standard and precision approaches in LT. If validated in LT, we foresee that the predictive approach to immunosuppression is readily translatable for evaluation in other solid organ transplantations. With over 125,000 solid organ transplantations being performed

worldwide annually, the clinical and economic implications of this study could be substantial.

c. BACKGROUND INFORMATION

i. SCIENTIFIC BACKGROUND

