As per **Figure 1**, 15-30ml will be collected to perform the QFM-dscfDNA testing and to be stored for future research purposes as per the extended consent obtained. Blood sampling will occur in the inpatient and outpatient setting at Austin Health, to ensure that investigators have direct and timely access to the blood samples. Blood samples will be processed in the Olivia Newtown John Cancer Research Institute (ONJCRI) and stored in a specially allocated -80°C freezer in the Liver Transplant Unit (LTU), both located at the same campus.

As per **Table 1**, blood will be collected pre-transplant (baseline) and post-transplant on days 1, 3 and 5; week 1 and 2; and months 1, 2, 4, 6 and 12 from enrolled participants (11 time points x 210 recipients = 2310 tests). We estimate that approximately 150 clinical events of acute rejection and infective complications will occur throughout the course of this study. As a standard of care, these clinical events require close surveillance with routine blood tests. In conjunction with the routine blood tests, additional blood will be sampled to capture the dynamics of QFMdscfDNA during these clinical events (3 time points taken 1-3 days apart, 3 x 150 events = 450 tests). A total of 2760 QFM-dscfDNA measurements will be performed in this study (2310 + 450 tests).

Table 1: Schedule of serial additional blood sampling			
Time		Additional blood sampling	
Before LT		x 1	
Post LT			
Day	1	x 1	
	3	x 1	
5		x 1	
Week	1	x 1	
	2	x 1	

Month	1	x 1
	2	x 1
	4	x 1
	6	x 1
	12	x 1
If a clinical event occurs		x 3 (taken 1-3 days apart)

The donor blood samples required for dscfDNA processing will be obtained during organ procurement, in accordance with the Human Research Ethics Committee for Donate Life and the Australian Red Cross Blood Services (application in progress).

iv. DATA COLLECTION, USE AND DISSEMINATION:

The following data (as defined in '**4.c OUTCOME MEASURES**' and '**5.a.iii INTERVENTION**') will be prospectively collected:

- Standard of care clinical variables
- Standard of care blood tests
- Clinical events
- Blood sampling
- Health expenditure

All data will be collected in identifiable form correlated to the patient's Austin Health UR, but will be re-identified or coded for use.

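### Both primary AUCs compare one event with all other recipients against a null of 0.5, so significance on both would not show that the tests can tell rejection from infection.

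*Protocol*

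**What the plan says.** - Section 4c (Primary Endpoints) sets one AUC for the first tBPAR and one for infection: "The first episode of infective complication, as measured by the AUC". QFM and dscfDNA, alone and combined, are compared with LFTs on each.
- Section 8a assumes N = 210 and event rates as follows: "we assume 30% of our recruited recipients will experience at least one tBPAR and 40% at least one infective complication". These come from preliminary work in which "31% of the recipients experienced tBPAR as the first event after LT" and "41% experienced a 'probable'/'definite' infective complication as the first event after LT".
- Section 8b gives 99.7% power for the combination to show "any ability to discriminate between those with and without tBPAR and 99.9% power between those with and without infection". The null AUC is 0.5, the assumed AUC 0.7 and alpha 5%.
- Section 8c puts all participants in the final analyses. It plans sensitivity, specificity, predictive values and AUC for each event, single tests against the combination, and joint models for each event type. None of these contrasts tBPAR with infection.
- Section 3b explains why the distinction matters: "Acute rejection is treated with increased doses of immunosuppressants while infection necessitates dosage reduction". It also describes LFTs as sensitive to organ injury but poorly specific for complications.
- Section 5a.iii already plans extra sampling at events: "3 time points taken 1-3 days apart, 3 x 150 events = 450 tests".

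**The concern.** The study question in the synopsis is how useful the tests are for monitoring and managing immunosuppression. Since the two events lead to opposite changes, a useful test must say which event is present, not only that the recipient is unwell.

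Under the primary contrasts, the 147 recipients without tBPAR include those with infection, and the 126 without infection include those with tBPAR. A score that rises equally in both events is penalised for this, but it still gains from every event-free control. Because the only stated null is 0.5, that gain can be enough for significance on both endpoints. The study could then report two positive primary results and draw a conclusion about managing immunosuppression that neither result supports.

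**Working it through.** **Inputs.** From 8a: N = 210; tBPAR 30% = 63, leaving 147 without; infection 40% = 84, leaving 126 without. From 8b: null 0.5, assumed AUC 0.7, alpha 5% (taken as two-sided, like the confidence interval). The protocol does not state how many recipients have both events, so that is varied below.

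**1. The protocol's own figures reproduce.** Binormal variance: with b = 1.414·Φ⁻¹(AUC) and k = non-cases/cases, V = 0.0099·exp(−b²/2)·[(5b²+8) + (b²+8)/k] and SE = √(V/cases).
- AUC 0.7: tBPAR 1.96 × 0.0415 = ±0.081; infection 1.96 × 0.0384 = ±0.075.
- AUC 0.8: ±0.075 and ±0.069.
- Power = Φ[(0.2 − 1.96·SE₀)/SE₁], where SE₀ is at AUC 0.5 and SE₁ at the assumed AUC: 99.7% to 99.8% for tBPAR (Hanley-McNeil and binormal variance) and 99.9% for infection.

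All agree with 8a and 8b.

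**2. A score blind to event type.** Let its AUC be 0.5 between tBPAR and infection, and *a* for either event against event-free recipients. An AUC against mixed controls is the weighted mean over the control types:
- tBPAR v rest = (infection-only × 0.5 + event-free × *a*) / 147
- infection v rest = (tBPAR-only × 0.5 + event-free × *a*) / 126

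With no overlap, event-free = 210 − 63 − 84 = 63. At *a* = 0.8:
- tBPAR: (84 × 0.5 + 63 × 0.8)/147 = 92.4/147 = 0.629
- infection: (63 × 0.5 + 63 × 0.8)/126 = 81.9/126 = 0.650

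**3. Power of that score against 0.5.** With the Hanley-McNeil variance:
- tBPAR: (0.1286 − 1.96 × 0.0436)/0.0432 = 1.00, power 84%
- infection: (0.150 − 1.96 × 0.0408)/0.0393 = 1.79, power 96%

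The binormal variance gives 86% and 97%. Rounded: about 85% and 96%.

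**4. What the same score needs to reach 0.7.**
- No overlap: tBPAR needs *a* = (0.7 × 147 − 84 × 0.5)/63 = 60.9/63 = 0.967. Infection needs (0.7 × 126 − 63 × 0.5)/63 = 56.7/63 = 0.900.
- Independent overlap (an assumption: 25.2 both, 37.8 tBPAR only, 58.8 infection only, 88.2 neither): tBPAR needs (102.9 − 29.4)/88.2 = 0.833. Infection needs (88.2 − 18.9)/88.2 = 0.786.
- Pilot first-event rates (31% and 41%, so 28% neither): tBPAR needs (0.7 × 0.69 − 0.5 × 0.41)/0.28 = 0.993.
- Background rates in section 3 (about 50% and 70%, independent): even *a* = 1 gives tBPAR only (0.35 × 0.5 + 0.15 × 1)/0.50 = 0.65, so 0.7 is out of reach.

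Simulation (1,000 runs per scenario) agrees. No overlap with *a* = 0.97 gives 0.702 and 0.734; independent overlap with *a* = 0.833 gives 0.700 and 0.735. The tBPAR-versus-infection AUC is 0.50 in both.

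**5. Feasibility of the missing contrast at AUC 0.7.** With 63 v 84 the half-width is about ±0.089 and power against 0.5 about 99%. With about 38 v 59 (recipients with both events set apart under independent overlap) it is about ±0.11 and about 93%.

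**The case against.** **The contrast matches the hypothesis.** Section 4a asks whether each event can be diagnosed, and with-versus-without is the right comparison for that. Keeping the other event among the controls also holds a blind score down: with no overlap its tBPAR AUC cannot exceed (84 × 0.5 + 63)/147 = 0.714. This stands, and the primary AUCs should stay as they are.

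**Other planned measures would partly expose such a score.** Take perfect separation from event-free recipients and no overlap. At the cut-off dividing event from no event, 147 recipients test positive. For tBPAR, specificity and positive predictive value are both 63/147 = 43%. For infection, specificity is 63/126 = 50% and positive predictive value 84/147 = 57%. The LFT comparison would also show no advantage for a score that only matched LFTs. But low specificity does not say which controls were misclassified, and the LFT comparison rests on the same mixed contrasts, so a score that merely separates unwell from well better than LFTs would still win.

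**The SAP may add the contrast.** It may; section 8c promises a detailed one. The point here is limited to what the protocol fixes: the two primary contrasts, their null, and the purpose they are meant to serve.

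**No treatment decision follows directly.** Results are batched and withheld from clinicians, and section 3b foresees a randomised trial next. This lowers the stakes, although the decision to run that trial would draw on these AUCs.

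A reader might infer that a blind test could easily clear a pass mark of 0.7 on both endpoints. The protocol does not support that: 0.7 is a planning value with no decision attached, and with no overlap reaching it on both needs about 0.97 against event-free recipients.

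**Conclusion.** The concern holds in a limited form. The primary contrasts are valid and the power and precision figures are correct, but significance on both endpoints is compatible with no ability to distinguish tBPAR from infection. The size is AUCs of 0.63 and 0.65 with about 85% and 96% power. This assumes the protocol's 30% and 40% rates, no overlap, a score distributed identically in the two events, and AUC 0.8 against event-free recipients. More overlap makes a blind score look better; higher event rates with fewer event-free recipients make it look worse. Neither an invalid primary analysis nor an arithmetic error can be inferred. This is an inexpensive improvement that would let the study address its own management question.

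**What to change.** In section 8c:

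1. Pre-specify, as a key secondary analysis, the AUC with 95% CI for first tBPAR versus first 'probable'/'definite' infection, for the combination and for LFTs. State how recipients with both events are handled, for example as a separate group.
2. Report each primary AUC by control type: event-free recipients, and recipients with the other event.
3. Limit conclusions about managing immunosuppression to what the tBPAR-versus-infection contrast shows. No fixed threshold for its lower confidence limit is needed; any such bar would be arbitrary.

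**Cost.** Additional wording and analysis only; the event samples are already in section 5a.iii, and no recipients are added. The contrast is less precise than the primary AUCs: at AUC 0.7, about ±0.089 with no overlap or about ±0.11 with overlapping recipients set apart, against ±0.081 and ±0.075. The headline may also be less favourable.

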The second test is a novel DNA-based laboratory assay based on the following concepts. Firstly, that during normal cellular turnover, the donor organ continuously sheds dscfDNA into the recipient circulation. Secondly, that when the donor organ is injured, dscfDNA increases. This can be quantified using next-generation sequencing techniques, however these are complex, labour-intensive and expensive¹²⁻¹⁴. Goh et al. therefore developed a polymerase chain reaction technique to quantify dscfDNA that is accurate, rapid and economic^{15,16}. They subsequently performed a pilot study in patients post LT comparing dscfDNA to clinical events, and found that dscfDNA levels were low in well patients, but elevated in those with tBPAR¹⁷.

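### The nadir is listed as a dscfDNA summary although the protocol says dscfDNA rises in rejection, and no peak or rise is listed

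*Protocol*

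**What the plan says.** Protocol 8.c gives one list of summaries for two markers. It opens with "Given that QFM and dscfDNA outcomes are measured repeatedly over 12 months" and then has both markers summarised "across time-points using the average, nadir, standard deviation and slope", for use in a logistic regression. The second stage reads "Next, we will look at moving average, moving standard deviation, and change of slope and fit a mixed logistic regression model", and a joint model follows. Neither stage lists a maximum, peak or rise from the previous sample.

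On direction, section 3.c.ii states that "when the donor organ is injured, dscfDNA increases", and reports from the pilot that "dscfDNA levels were low in well patients, but elevated in those with tBPAR".

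On the assay, section 4.c says that genotyping identifies "allelic sequences that are present in the donor and absent in the recipient for the detection of dscfDNA".

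On timing, section 5.a.iii says that "blood will be collected pre-transplant (baseline) and post-transplant on days 1, 3 and 5", followed by later visits to month 12. The pre-transplant draw is one of the 11 time points multiplied by 210 recipients in the test count. Three further samples are taken for each clinical event.

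**The concern.** An extreme value is a useful summary only if it lies on the side to which the marker moves. A low QFM plausibly reflects weak immune function, so a nadir is reasonable there. For dscfDNA the protocol describes the opposite movement: quiet when well, high in tBPAR. The 12-month minimum records each recipient's quietest sample, which a rejection episode does not alter.

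The pre-transplant sample adds to this. A test for sequences that the recipient does not carry should read zero, apart from assay background, before the graft is in place. If that value enters the summary, the minimum is fixed at the floor.

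The AUC of dscfDNA, alone and combined with QFM, for the first tBPAR is a primary endpoint. At stake is whether the first planned model spends one of its four dscfDNA predictors on a near-constant and omits the extreme that matches the hypothesis.

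**Working it through.** **The plan's own figures.** Scheduled tests: 1 pre-transplant + 10 post-transplant = 11 time points; 11 × 210 = 2310. Event tests: 3 × 150 = 450. Total: 2310 + 450 = 2760, as stated. The total reaches 2760 only if the 210 pre-transplant samples count as QFM-dscfDNA measurements. The AUC half-widths in 8.a also reproduce, with the binormal variance formula and 63/147 (tBPAR) or 84/126 (infection) cases/non-cases: 0.0813 and 0.0752 at AUC 0.7, and 0.0754 and 0.0690 at AUC 0.8. None of these figures is disputed.

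**Nadir with the pre-transplant value.** min(0, x₁, …, x₁₀) = 0 for every recipient when all x ≥ 0. All case/non-case pairs are then tied, each tie counts ½, and AUC = 0.50. Assay background would turn this into noise around the floor.

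**Nadir without it.** If a rise affects only some samples, the minimum comes from the unaffected ones, so cases and non-cases have about the same distribution of minima.

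**Illustrative simulation.** Assumed, not from the protocol: log-scale within-patient SD 0.5; between-patient SD 0 or 0.5; a 3-, 5- or 10-fold rise in the three event samples, taken from day 7 to 90; with or without a high early post-transplant value in everyone. From the protocol: 63 of 210 cases and the sampling schedule. Ranges of mean AUC:

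| dscfDNA summary over the whole period | No early elevation | Early elevation |
|---|---|---|
| Nadir, pre-transplant value included | 0.500 | 0.500 |
| Nadir, post-transplant only | 0.496–0.506 | 0.493–0.504 |
| Average | 0.702–1.000 | 0.586–0.995 |
| SD | 0.805–1.000 | 0.536–0.973 |
| Peak | 0.816–1.000 | 0.554–0.962 |

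The last three rows include the pre-transplant zero. They also pool three extra samples that only cases have, so they show which summaries respond to a rise and do not forecast accuracy. A whole-period peak is not clearly better than the SD, and early post-operative values degrade both. A windowed peak was not simulated.

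**Effect of the zero on the other summaries.** With 10 post-transplant samples, a zero multiplies each average by 10/11 = 0.909. With 13 (one event) the factor is 13/14 = 0.929. The ratio is (13/14)/(10/11) = 143/140 = 1.021, about 2%. A common factor does not change ranks, so only this 2% difference can. In simulation under the same assumptions, including the zero moved the AUC of the average by at most 0.03 and of the SD by at most 0.025. The slope was pulled towards 0.5 by up to about 0.08.

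**The case against.** The strongest reply is that this is an opening step that the plan itself supersedes. The average and SD already respond to a rise. Moving summaries, a mixed model and a joint model come next. A detailed SAP is promised before database lock, and the protocol does not say that its list is exhaustive. A constant predictor adds nothing to a logistic model but does not bias the rest. Much of this stands, and it limits the consequence. It does not remove the point, because the protocol names the summaries and chooses an extreme that contradicts its own account of the marker.

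Several stronger readings are tempting but are not supported:

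- That the dscfDNA nadir is certainly tied in all 210 recipients. The protocol never says that the pre-transplant value enters the summaries. The count of 11 is a workload figure, and section 4.c gives the pre-transplant recipient sample a genotyping role.
- That one zero in 11 values (9%) distorts every average. It mainly rescales them and hardly changes ranks.
- That the study will wrongly find dscfDNA of little value. The other summaries can still show a rise, and setting one predictor's AUC of 0.5 against the planning values of 0.7 and 0.8 compares unlike things.
- That the peak is right for both primary events. The documents state the direction of dscfDNA for graft injury and tBPAR, not for infection.

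**Conclusion.** The point holds for dscfDNA and tBPAR. The nadir carries little or no information there (AUC about 0.5), whether or not the pre-transplant sample is included, and the extreme that matches the stated biology is not listed. That conclusion rests on the protocol's own statement of direction and on the rise being transient; the simulation only illustrates it. Including the pre-transplant value would also attenuate the slope, but that inclusion is an inference. The loss to the primary analysis cannot be put as a figure from the documents. It is a weakness in the first modelling step that is worth correcting, and it does not invalidate the dscfDNA analysis.

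**What to change.** Amend 8.c so that the extreme is chosen by marker:

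- Keep the nadir for QFM.
- For dscfDNA and tBPAR, replace it with the peak, or the rise over the previous sample. Take it from post-transplant samples in a window ending at the event, or at a matched time in non-cases.
- Base it on comparable numbers of samples in cases and non-cases, so that early post-operative values and the three extra event samples do not drive it.
- Exclude the pre-transplant value from all dscfDNA summaries.

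The cost is a written matching rule for non-cases and a little more analysis. No new samples or assays are needed. Because the assays are batched after each recipient's 12-month follow-up, the rule can be fixed before any result is read, which avoids a data-driven choice of summary.
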